14.2.1 Rationale for the amendment

The second SAP amended has been developed to include some requirements observed during the study Dry Run as well as to include the ad-hoc outputs which were not part of the initial SAP. Updates made in the CRF are also described here. Few other minor formatting updates were made.

14.2.2 List of changes

Specific changes

Change #1

General along the document

In some places, “timepoint” has been changed to “visit” to make the text more appropriate to how the data is collected; hence “timepoint” is now only referring to a “moment of time” within a visit or to a general moment during the study conduction.

Change #2

Definition of Baseline values (Section 3.3)

Baseline will be the last available predose value prior to the first infusion of UCB7665, or if missing, the Screening values.

Measurement-specific Baseline timepoints (based on the planned measurements) are presented in [Table 3–1](#).

Table 14–1: Definition of Baseline

Measurement	Definition of Baseline

Safety data:
 
 • Clinical chemistry (including proteins) • Hematology (including platelets measured locally) • Coagulation • Urinalysis • Vital signs • 12-lead ECG • Serum safety biomarkers [REDACTED] 	
 • Predose Day 1 or if missing the Screening value^a

Efficacy variables:
 
 • Platelets (measured by ACM Global Central Laboratory) • ITP bleeding scale • NFI-MS 	
 • Platelets: Predose Day 1 or if missing the Screening value • ITP bleeding scale: Predose Day 1 or if missing the Screening assessment • NFI-MS: Predose Day 1

Pharmacodynamic variables:
 
 • Total IgG • IgG subclasses • ITP-specific autoantibodies in serum [REDACTED] 	
 • Total IgG: Predose Day 1 or if missing the Screening value • IgG subclasses: Predose Day 1 or if missing the Screening value • ITP-specific autoantibodies: Predose Day 1

Immunological variables:
 
 • Immunoglobulins (IgA, IgE and IgM) • B- and T-lymphocytes • Serum (C3 and C4) and plasma complement (C3a and C5a) • ADA • Serum BAFF • Cytokines, if applicable (as outlined in the protocol) 	
 • Predose Day 1 (except B- and T-lymphocytes) • B- and T-lymphocytes: Predose Day 1 or if missing the Screening value

If the Screening value is to be used as Baseline (i.e., predose Day 1 is missing), the highest value for the platelet count obtained from the 2 measurements at Screening will be used as the Baseline.

Has been changed to:

Baseline will be the last available predose value prior to the first infusion of UCB7665, or if missing, the latest no missing value prior to Baseline (screening value or unscheduled visit value).

Measurement-specific Baseline timepoints (based on the scheduled or unscheduled measurements) are presented in [Table 3–1](#).

Table 14–1: Definition of Baseline

Measurement	Definition of Baseline

Safety data:
 
 • Clinical chemistry (including proteins) • Hematology (including platelets measured locally) • Coagulation • Urinalysis • Vital signs • 12-lead ECG • Serum safety biomarkers [REDACTED] [REDACTED] [REDACTED] 	
 • Predose Day 1 or if missing the latest no missing value prior to Day 1

Efficacy variables:
 
 • Platelets (measured by ACM Global Central Laboratory) • ITP bleeding scale • NFI-MS 	
 • Platelets: Predose Day 1 or if missing the latest no missing value prior to Day 1 • ITP bleeding scale: Predose Day 1 or if missing the latest no missing value prior to Day 1 • NFI-MS: Predose Day 1

Pharmacodynamic variables:
 
 • Total IgG • IgG subclasses • [REDACTED] • ITP-specific autoantibodies in serum [REDACTED] 	
 • Total IgG: Predose Day 1 or if missing the latest no missing value prior to Day 1 • IgG subclasses: Predose Day 1 or if missing the latest no missing value prior to Day 1 • ITP-specific autoantibodies: Predose Day 1

Immunological variables:
 
 • Immunoglobulins (IgA, IgE and IgM) • B- and T-lymphocytes • Serum (C3 and C4) and plasma complement (C3a and C5a) • ADA • Serum BAFF • Cytokines, if applicable (as outlined in the protocol) 	
 • Predose Day 1 (except B- and T-lymphocytes) • B- and T-lymphocytes: Predose Day 1 or if missing the latest no missing value prior to Day 1

If the latest non missing value prior to Baseline is to be used as Baseline (i.e., predose Day 1 is missing), the highest value for the platelet count obtained from the last 2 non missing measurements prior to Baseline will be used as the Baseline.

Change #3

Electrocardiogram data (Section 4.2.6)

For the ECG data, all calculations of changes from Baseline and descriptive statistics will be based on the mean of the triplicate assessments at each timepoint. In the event that there are not 3 available measurements at a given timepoint, the mean will be calculated based on the number of measurements for which data is provided.

Has been changed to:

For the ECG data, all calculations of changes from Baseline and descriptive statistics will be based on the mean of the triplicate assessments at each visit. In the event that there are not 3 available measurements at a given visit, the mean will be calculated based on the number of measurements for which data is provided (variables analyzed will be those described in Section 10.4.2).

Change #4

Examination of subgroups (Section 4.8)

The following subgroups will be defined within each dose arm:

- Use of corticosteroid medication: Present
- Use of corticosteroid medication: Absent
- Responder at the end of previous ITP treatment: No
- Responder at the end of previous ITP treatment: Yes

Only medication classified as either 'prior and concomitant' or 'concomitant' and medical procedure will be considered for ITP treatment. Responder categories will be defined taking into account the last valid value reported (either Yes or No) for each patient. Past use of corticosteroids (not ongoing after dosing) will not be considered for this classification. The list of applicable Anatomical Therapeutic Chemical (ATC) codes in order to identify the presence/absence of corticosteroids is provided in Section 13.1.

Has been changed to:

The following subgroups will be defined within each dose arm:

- Use of corticosteroid medication: Present/Absent
- Responder at the end of previous ITP treatment: No/Yes/Unknown
- Previous intravenous immunoglobulin (IVIg) therapy: Yes/No
- Number of previous ITP therapies: ≤ 2 / > 2

Only medication classified as either 'prior and concomitant' or 'concomitant' and medical procedure will be considered for ITP treatment. Responder categories will be defined taking into account the last reported ITP treatment value (either Yes or No) for each patient. If this value is

unknown, the second-last reported ITP treatment value will be used, then the third-last, and so on, until a known response is provided. The Unknown responder category will only be considered in cases where the investigator has never reported a category (Yes or No) for any of the previous ITP treatments. Past use of corticosteroids (not ongoing after dosing) will not be considered for this classification. The list of applicable Anatomical Therapeutic Chemical (ATC) codes in order to identify the presence/absence of corticosteroids is provided in [Section 13.1](#).

Change #5

Demographics (Section 6.1)

All Baseline demographic characteristics (with the exception of year of birth) will be summarized by dose arm and overall for the SS.

Has been changed to:

All Baseline demographic characteristics (with the exception of year of birth) will be summarized by dose arm and overall for the SS. Number and percentage of patients with a BMI equal or higher than 30 will also be summarized by dose arm.

Change #6

Other Baseline characteristics (Section 6.2)

Baseline disease characteristics will be listed and summarized by dose arm for the SS including the following:

- Duration of disease
- Karnofsky Performance Scale Index
- ITP bleeding scale (skin, visible mucosae and organs, with gradation of severity [SMOG])
- ITP-specific autoantibodies [REDACTED] expressed in terms of optical density (OD) for MAIPA analysis and pre-chloroquine minus post chloroquine treated scores for PIFT
- Immunological variables (IgG [including total IgG and IgG subclasses measured by ACM Global Central Laboratory], IgM, IgA, IgE and lymphocytes [B and T])
- Serum (C3 and C4) and plasma complement levels (C3a and C5a)
- Platelet count (measured by ACM Global Central Laboratory)

Has been changed to:

Baseline disease characteristics will be listed and summarized by dose arm for the SS including the following:

- Duration of disease
- Karnofsky Performance Scale Index
- ITP bleeding scale (skin, visible mucosae and organs, with gradation of severity [SMOG])

- ITP-specific autoantibodies [REDACTED] expressed in terms of optical density (OD) for MAIPA analysis and pre-chloroquine minus post chloroquine treated scores for PIFT
- Immunological variables (IgG [including total IgG and IgG subclasses measured by ACM Global Central Laboratory], IgM, IgA, IgE and lymphocytes [B and T])
- Serum (C3 and C4) and plasma complement levels (C3a and C5a)
- Platelet count (measured by ACM Global Central Laboratory)
- Number of prior ITP medications received
- Number of prior ITP medications received categorized
- Prior ITP medications received by preferred term
- Medical history of splenectomy (MedDRA v20.2, Preferred Term="Splenectomy")

Change #7

Measurements of treatment compliance (Section 7)

The study medication will be administered and monitored by the investigator or designee. The measured plasma concentrations will provide information regarding compliance. Any dosing deviations (eg, incomplete infusion volume administered, infusion temporarily interrupted, infusion discontinued) will be discussed at the DEM and any actions taken regarding the analyses will be documented accordingly and discussed in the CSR.

Has been changed to:

The study medication will be administered and monitored by the investigator or designee. The measured plasma concentrations will provide information regarding compliance. Any dosing deviations (eg, incomplete infusion volume administered, infusion discontinued) will be discussed at the DEM and any actions taken regarding the analyses will be documented accordingly and discussed in the CSR.

Change #8

Platelets (Section 8.1)

All efficacy analyses are based on platelet count measured by ACM Global Central Laboratory. Measurements of platelet count obtained by the local laboratory will be listed and summarized as part of the safety laboratory data. These are not included in the analyses described in the sections below. All tabulations and mean figures will be presented for both the FAS and the PPS unless otherwise stated. Individual figures will be presented for the FAS only. In case rescue medications are taken, only the platelet data up to the time point where the rescue medication is taken will be utilized.

Has been changed to:

All efficacy analyses are based on platelet count measured by ACM Global Central Laboratory. Measurements of platelet count obtained by the local laboratory will be listed and summarized as part of the safety laboratory data. These are not included in the analyses described in the sections below. All tabulations and mean figures will be presented for both the FAS and the PPS unless

otherwise stated. Median figures and individual figures will be presented for the FAS only. In case rescue medications are taken, only the platelet data up to the time point where the rescue medication is taken will be utilized for the summary tables. Listings will contain all the data but a footnote will be included indicating the patients for which some data has been excluded from the summary tables.

Change #9

Presentation of results (Section 8.1.2)

The individual platelet measurements will be listed by dose arm and timepoint including changes from Baseline (Day 1, predose). Descriptive summaries (including n, arithmetic mean, median, SD, minimum and maximum) will be presented by dose arm and scheduled timepoint for both absolute values and changes from Baseline. Summary tabulations by dose arm will be repeated for the subgroups defined in [Section 4.8](#) (based on the FAS only).

Has been changed to:

The individual platelet measurements will be listed by dose arm and visit including changes from Baseline (Day 1, pre-dose). Descriptive summaries (including n, arithmetic mean, median, SD, minimum and maximum) will be presented by dose arm and scheduled visit for both absolute values and changes from Baseline based on the FAS only. Summary tabulations by dose arm will be repeated for the subgroups defined in [Section 4.8](#) (based on the FAS only too).

Change #10

Presentation of results (Section 8.1.2)

Mean and mean change from Baseline platelet values will be plotted versus scheduled visit by dose arm with all dose arms overlaid on the same plot. Similar plots will be provided for response rate over time (response, complete response and platelet count $\geq 50 \times 10^9/L$).

Individual platelet and total IgG (including IgG subclasses, measured by ACM Global Central Laboratory) concentrations will be displayed graphically over time (Day 1 to Day 85 for Dose Arm 1; Day 1 to Day 71 for Dose Arm 2; Day 1 to Day 64 for Dose Arm 3 and Day 1 to Day 57 for Dose Arms 4 and 5) for each subject (linear scale). The platelet and total IgG concentrations will be overlaid on the same plot (discrete y-axes) with separate plots for each subject (2 lines per plot). Additional plots will be presented with the platelet and IgG subclasses overlaid on the same figure (5 lines per plot). All plots will include a vertical reference line to indicate when the last dose was administered for each subject.

Has been changed to:

Mean and mean change from Baseline platelet values will be plotted versus scheduled visit by dose arm with all dose arms overlaid on the same plot. Similar plots will be provided for response rate over time (response, complete response and platelet count $\geq 50 \times 10^9/L$). Mean median, mean change and median change from Baseline total IgG results will be plotted over time by dose arm with all dose arms overlaid on the same plot.

Individual platelet and total IgG (including IgG subclasses, measured by ACM Global Central Laboratory) concentrations will be displayed graphically over time (Day 1 to Day 85 for Dose Arm 1; Day 1 to Day 71 for Dose Arm 2; Day 1 to Day 64 for Dose Arm 3 and Day 1 to Day 57 for Dose Arms 4 and 5) for each subject (linear scale). The platelet and total IgG concentrations

will be overlaid on the same plot (discrete y-axes) with separate plots for each subject (2 lines per plot). Additional plots will be presented with the platelet and IgG subclasses overlaid on the same figure (5 lines per plot). All plots will include a vertical reference line to indicate when the last dose was administered for each subject. The mean (and median in a separate plot) change from baseline in platelet and the mean (median) change from baseline in total IgG concentrations will be overlaid on the same plot (discrete y-axes) with separate plots for each dose arm (2 lines per plot).

Change #11

Analysis of responder rate (Section 8.1.3.3)

The following paragraphs have been added at the end of this subsection:

Moreover, for responder rate, summary tabulations by dose arm will be repeated according to previous intravenous immunoglobulin therapy (Yes/No) and the number of previous medications (≤ 2 / > 2). Percentage of days without bleeding will also be described by dose arm for each type of response (response, complete response and platelet Count $\geq 50 \times 10^9/L$). Percentage of days without bleeding is calculated using the following formula:

$$\frac{((N \text{ of visits with a SMOG score} - N \text{ of these visits where bleeding occurred}) / N \text{ of visits with a SMOG score}) \times 100$$

In case rescue medications are taken, only the data up to the start date of rescue medication will be utilized for the summary tables. Listings will contain all the data but a footnote will be included indicating the patients for which some data has been excluded from the summary tables. In case of partial dates, the imputation rules for partial dates described in Section 4.2.7 will be applied.

Change #12

IPT bleeding score and platelet response (Section 8.2.1.1)

All response variables described above will be listed by dose arm and subject and summarized by dose arm and visit where appropriate. The responder rates will be tabulated as described in Section 8.1.3.3. All analyses described in this section will be performed for the FAS.

Has been changed to:

All response variables described above will be listed by dose arm and subject and summarized by dose arm and visit where appropriate. The responder rates will be tabulated as described in Section 8.1.3.3. Moreover the change in category of bleeding from Baseline will also be presented in shift table at all post-Baseline timepoints by dose arm. Summary tabulations for Clinical Response by dose arm will be repeated according to previous intravenous immunoglobulin therapy (Yes/No) and the number of previous medications (≤ 2 / > 2). All analyses described in this section will be performed for the FAS.

In case rescue medications are taken, only the data up to the start date of rescue medication will be utilized for the summary tables. Listings will contain all the data but a footnote will be included indicating the patients for which some data has been excluded from the summary tables. In case of partial dates, the imputation rules for partial dates described in Section 4.2.7 will be applied.

Change #13

Pharmacokinetics (Section 9.1)

The following sentence has been removed from this section:

If applicable, a separate listing of UCB7665 concentrations in the cerebrospinal fluid (CSF) will be presented by dose arm. These data will not be summarized.

Change #14

ITP-specific autoantibodies (Section 9.2.1)

The results will be expressed in the form of the OD value.

ITP-specific autoantibodies (OD value) will be listed by dose arm and timepoint. Values that are ALD will be displayed as such in the listings.

Has been changed to:

The results will be expressed in the form of the OD value and for indirect PIFT method using the following categories: 0 = negative; 0.5 = weak positive; 1 = positive; 2 = positive; 3 = strong positive; 4 = strong positive.

ITP-specific autoantibodies (OD value and PIFT categories) will be listed by dose arm and timepoint. OD values that are ALD will be displayed as such in the listings.

Change #15

ITP-specific autoantibodies (Section 9.2.1)

The following sentence has been added at the end of this section:

Only patients with positive ITP-specific autoantibodies will be described.

Change #16

Total IgG and IgG subclasses (Section 9.2.2)

Mean and mean percentage change from Baseline values in total IgG (measured by ACM Global Central Laboratory) will be plotted over time by dose arm with all dose arms overlaid on the same plot. Additional figures will be presented in conjunction with the ADA results as described in [Section 9.3.4](#) as well as figures in conjunction with the platelet results as described in [Section 8.1.1](#).

Finally, a separate figure will be presented by subject showing the individual total IgG results from ACM Global Central Laboratory.

Any values that are BLQ or ALQ will be handled as described in [Section 4.2.32](#).

All analyses described in this section will be performed on the PD-PPS. In case rescue medications are taken, only the IgG data up to the timepoint where the rescue medication is taken will be utilized for the summary tables. Listings will contain all the data but a footnote will be included indicating the patients for which some data has been excluded from the summary tables.

Has been changed to:

Mean, median, median change from Baseline and mean and median percentage change from Baseline values in total IgG (measured by ACM Global Central Laboratory) will be plotted over time by dose arm with all dose arms overlaid on the same plot. Additional figures will be presented in conjunction with the ADA results as described in [Section 9.3.4](#) as well as figures in conjunction with the platelet results as described in [Section 8.1.1](#).

Finally, a separate figure will be presented by subject showing the individual total IgG results from ACM Global Central Laboratory.

Any values that are BLQ or ALQ will be handled as described in [Section 4.2.3](#).

All analyses described in this section will be performed on the PD-PPS. In case rescue medications are taken, only the IgG data up to the start date of rescue medication will be utilized for the summary tables. Listings will contain all the data but a footnote will be included indicating the patients for which some data has been excluded from the summary tables. In case of partial dates, the imputation rules for partial dates described in [Section 4.2.7](#) will be applied.

Change #17

Adverse events (Section 10.2)

In addition the listing will flag AEs that led to discontinuation, TEAEs, AEs of interest, AEs of special interest, infusion reactions and SAEs.

Has been changed to:

In addition the listing will flag AEs that led to discontinuation, TEAEs, AEs of interest, AEs of special interest, infusion reactions, SAEs, Sampson criteria and CTCAE grade.

Change #18

Clinical laboratory evaluations (Section 10.3)

Values outside the reference range for the numeric variables will be flagged in the listings and in addition, will be listed separately. The reference ranges will also be reported in the listings.

Has been changed to:

Values outside the reference range for the numeric variables will be flagged in the listings and in addition, results considered as markedly abnormal laboratory results (CTCAE Grade 3 and above) will be listed separately. The reference ranges will also be reported in the listings.

Change #19

Vital signs (Section 10.4.1)

Table 10-2 has been updated as follows:

Variable	Unit	Low	High
Systolic blood pressure	mmHg	Value <90 and ≥20 decrease from Baseline	Value >180 and ≥15 increase from baseline
Diastolic blood pressure	mmHg	Value <50 and ≥15 decrease from Baseline	Value >105 and ≥15 increase from Baseline

Change #20

Electrocardiograms (Section 10.4.2)

The following sentence has been added at the end of this subsection:

The number and percentage of subjects with TEMA/PCS ECG values will be summarized by dose arm at each timepoint.

Change #21

Electrocardiograms (Section 10.4.2)

- QT corrected for heart rate using Fridericia’s formula (QTcF)

The individual measurements and the mean of the triplicate measurements will be reported in the by-subject listings. The listing will also include the change from Baseline and percentage change from Baseline (based on the mean of the triplicate measurements at each timepoint) and will be presented by dose arm and timepoint.

Has been changed to:

- QT corrected for heart rate using Fridericia’s formula ($QTcF = QT/RR^{0.33}$)

The individual measurements and the mean of the triplicate measurements will be reported in the by-subject listings. The listing will also include the change from Baseline and percentage change from Baseline (based on the mean of the triplicate measurements at each timepoint). TEMA/PCS ECG values will be flagged in the listing.

Change #22

Electrocardiograms (Section 10.4.2)

The following table has been added:

Variable	Criteria
QT corrected for heart rate using Fridericia’s formula (QTcF)	≥501ms OR ≥60ms compared to baseline
PR prolongation	≥210ms and ≥10ms change from baseline

Change #23

Classification of markedly abnormal laboratory values based in CTCAE grades (Section 13.5)

Table 13-2 has been updated as follows:

Category	Panel	Variable	Criteria (CTCAE ^a Grade 3 and above)
Hematology	Red blood cell	Hemoglobin (Decrease)	<8g/dL (<80g/L)

Category	Panel	Variable	Criteria (CTCAE ^a Grade 3 and above)
		Hemoglobin (Increase)	>4g/dL (>40g/L) above ULN OR >4g/dL (>40g/L) above baseline if baseline is > ULN
	White blood cell	WBC count (Decrease)	<2000/mm ³ (<2.0x10 ⁹ /L)
		WBC count (Increase)	>20,000/mm ³
	White blood cell differential	ALC (Decrease)	<500/mm ³ (<0.5x10 ⁹ /L)
		ALC (Increase)	>20,000/mm ³ (>20x10 ⁹ /L)
		ANC	<1000/mm ³ (<1.0x10 ⁹ /L)
Chemistry	Liver Function	ALT	≥5.0xULN
		ALP	>5.0xULN
		AST	>5.0xULN
		Total bilirubin	>3.0xULN
		GGT	>5.0xULN
	Kidney Function	Creatinine	>3.0xbaseline value OR >3.0xULN
		Creatinine (Acute kidney injury)	>3xbaseline value OR >4xULN
		Creatinine phosphokinase	>5xULN
		eGFR or CrCl	≤29ml/min/1.73m ²
	Minerals	Calcium (Decrease)	corrected <7mg/dL (<1.75mmol/L); ionized <0.9 mmol/L
		Calcium (Increase)	corrected >13.5mg/dL (>3.1mmol/L); ionized >1.8mmol/L
		Magnesium (Decrease)	<0.4mmol/L (<0.9mg/dL)
		Magnesium (Increase)	>1.23mmol/L (>3mg/dL)
		Phosphate	<0.6mmol/L (<2mg/dL)
	Metabolic	Glucose (Decrease)	<2.2mmol/L (<40mg/dl)

Category	Panel	Variable	Criteria (CTCAE ^a Grade 3 and above)
		Glucose (Increase)	>250mmol/L (>13.9mg/dl)
	Electrolytes	Potassium (Decrease)	<3.0mmol/L
		Potassium (Increase)	>6.0mmol/L
		Sodium (Decrease)	<130mmol/L
		Sodium (Increase)	>155mmol/L
	Lipids	Total cholesterol	>10.34mmol/L (>400mg/dL)
		Triglycerides	>5.7mmol/L (>500mg/dL)
	Proteins	Albumin	<20g/L (<2g/dL)
	Other	Amylase	>2.0xULN

14.3 Amendment 3

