10.3 Clinical laboratory evaluations

Laboratory data (chemistry [excluding follicle stimulating hormone, FSH], hematology, coagulation and urinalysis) and changes from Baseline (if applicable) for numeric variables will

be listed by dose arm and visit. Any laboratory measurements that are BLQ or ALQ will be handled as described in Section 4.2.2. Values outside the reference range for the numeric variables will be flagged in the listings and in addition, results considered as markedly abnormal laboratory results (CTCAE Grade 3 and above) will be listed separately. The reference ranges will also be reported in the listings.

Chemistry [excluding FSH], hematology and coagulation variables will be summarized by dose arm at each visit, for both absolute values and changes from Baseline.

Laboratory variables will be grouped according to the laboratory function panel (Table 10-1) and categorized as normal, high or low, if applicable, based on the reference range supplied by the analytical laboratory. For selected variables that are identified in Table 10-1, the change in category from Baseline will be presented in shift tables at all post-Baseline visits.

Table 10–1: Clinical laboratory measurements

Category	Panel	Variable
Serology	Serology	HIV, HBsAg, anti-HBs, anti-HBc, anti-HCV
Hematology	Red blood cell	RBC count ^a , hemoglobin ^a , hematocrit
	Platelet	Platelet ^{ab}
	White blood cell	WBC count ^a
	White blood cell differential	Absolute counts: ANC ^a , basophils ^a , eosinophils ^a , ALC ^a , monocytes ^a Percentages: neutrophils/leukocytes ^a , basophils/leukocytes ^a , eosinophils/leukocytes ^a , lymphocytes/leukocytes ^a , monocytes/leukocytes ^a .
Coagulation	Coagulation	INR ^a , prothrombin time ^a , aPTT ^a , fibrinogen ^a
Chemistry	Electrolytes	Sodium ^a , chloride ^a , potassium ^a
	Minerals	Calcium ^a , phosphate ^a , magnesium ^a
	Kidney function	BUN ^a , creatinine ^a
	Proteins	Total protein ^a , albumin ^a , α1-globulin ^a , α2-globulin ^a , β-globulin ^a , gamma globulin ^a . For all parameters except total protein, both absolute and percentage values will be reported as part of the serum protein electrophoresis.
	Liver function	AST ^a , ALT ^a , GGT ^a , ALP ^a , LDH ^a , total bilirubin ^a , direct bilirubin (if indicated)
	Lipids	Total cholesterol ^a , triglycerides ^a
	Hormones	FSH
	Other	hsCRP ^a , amylase ^a
Urinalysis	Dipstick	pH ^a , protein, glucose, ketones, urobilinogen, bilirubin, blood, nitrite, leucocytes

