Category	Panel	Variable
	Quantitative	Albumin, creatinine
	Urine sediment ^c	RBC, WBC, epithelial cells, casts, crystals, yeast, bacteria, amorphous urates, amorphous phosphates
Pregnancy test		Urine HCG ^d , serum HCG ^e
Other		HbA1c

ALC=absolute lymphocyte count; ALP=alkaline phosphatase; ALT=alanine aminotransferase; ANC=absolute neutrophil count; anti-HBc=hepatitis B core antibody; anti-HBs=hepatitis B surface antibody; anti-HCV=hepatitis C virus antibody; aPTT=activated partial thromboplastin time; AST=aspartate aminotransferase; BUN=blood urea nitrogen; FSH=follicle stimulating hormone; GGT=gamma-glutamyltransferase; HbA1c=glycosylated hemoglobin; HBsAg=hepatitis B surface antigen; HCG=human chorionic gonadotropin; HIV=human immunodeficiency virus; hsCRP=high sensitivity C-reactive protein; INR=International Normalized Ratio; LDH=lactate dehydrogenase; RBC=red blood cell; TB=tuberculosis; WBC=white blood cell.

^a Shift tables will be presented for these variables.

^b Only platelet results measured at the local laboratory will be included in the safety outputs. Measurements obtained at the central laboratory will be reported as part of the efficacy analyses.

^c If indicated, based on results of urine dipstick.

^d Urine pregnancy test will be performed predose on dosing days and at the End-of-Study Visit

^e Serum pregnancy test is done at Visit 1 (Screening) and to confirm results of positive urine test if applicable.

The number and percentage of subjects with markedly abnormal laboratory results (CTCAE Grade 3 and above) will be tabulated by dose arm and laboratory variable at each visit. The criteria for identifying abnormal laboratory results are detailed in [Section 13.5](#).

Figures of mean and mean change from Baseline will be plotted over time by dose arm for all quantitative laboratory variables (with the exception of any variables measured only at Screening and/or Baseline, eg serology, HbA1c and FSH), with all dose arms overlaid on the same plot. The reference range for each variable (male and female, if applicable) will be included on the plot for absolute values. For the differential WBC counts, figures will be presented based on percentage values only.

Any additional laboratory variables not included in the outputs described previously (including pregnancy testing, FSH and serology) will be listed separately.

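### The high-calcium limit in the updated Table 13-2 pairs two values that are not equal, so who counts as markedly abnormal depends on which half is programmed; the high-glucose line has its unit labels exchanged

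*SAP*

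**What the plan says.** Section 14.2.2, Change #23, opens with "Table 13-2 has been updated as follows" and then gives the table of limits for CTCAE Grade 3 and above. Four of its lines matter here:

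- Calcium, low: "corrected <7mg/dL (<1.75mmol/L); ionized <0.9 mmol/L"
- Calcium, high: "corrected >13.5mg/dL (>3.1mmol/L); ionized >1.8mmol/L"
- Glucose, low: "<2.2mmol/L (<40mg/dl"
- Glucose, high: ">250mmol/L (>13.9mg/dl"

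This is the adopted text of that amendment, not the text it replaced. None of Changes #1 to #18 in Amendment 3 (Section 14.3.2) concerns Table 13-2 or Section 13.5.

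Section 10.3 puts the limits to two uses. In the listings, "results considered as markedly abnormal laboratory results (CTCAE Grade 3 and above) will be listed separately". In the tables, "The number and percentage of subjects with markedly abnormal laboratory results (CTCAE Grade 3 and above) will be tabulated by dose arm", by laboratory variable and visit. For the limits themselves it refers to Section 13.5: "The criteria for identifying abnormal laboratory results are detailed in" that section.

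Table 10-1 includes calcium in the chemistry panel under minerals. It has no blood glucose; glucose appears only among the urine dipstick items.

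**The concern.** A limit printed in two units must be one limit. If the halves differ, the plan contains two rules, and the programmer chooses between them by choosing a unit. For calcium the choice moves the threshold within a planned analyte. For glucose, the mg/dL half of the high rule is lower than the low limit, so the line cannot work as printed.

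At stake are the Grade 3 and above counts by dose arm. The arms are small (Section 2.3), so one subject moves an arm's percentage at a visit noticeably: 1/15 = 6.7 points in Dose Arms 1 and 2, and 1/12 = 8.3 to 1/6 = 16.7 points in Dose Arms 3 to 5, if all subjects in the arm are measured.

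**Working it through.** **Inputs.** All limits come from Change #23. Conversion uses mg/dL = mmol/L × molar mass / 10, with assumed physical constants for glucose (180.156 g/mol, factor 18.016) and calcium (40.078 g/mol, factor 4.008). As a check that needs no outside figure, the table's own low-side pairs imply 40 / 2.2 = 18.18 for glucose and 7 / 1.75 = 4.00 for calcium.

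**1. Low lines, reproduced first.**
- Calcium: 7 / 4.008 = 1.747 mmol/L; printed 1.75. Agrees.
- Glucose: 40 / 18.016 = 2.220 mmol/L; printed 2.2. Agrees.

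**2. High calcium.**
- 13.5 / 4.008 = 3.37 mmol/L (13.5 / 4.00 = 3.375 on the table's own factor); printed 3.1.
- 3.1 × 4.008 = 12.42 mg/dL (3.1 × 4.00 = 12.4); printed 13.5.
- Gap: (13.5 − 12.42) / 12.42 = 8.7%.
- Rounding: 3.37 to one decimal is 3.4. A printed 3.1 covers 3.05 to 3.15 mmol/L, which is 12.2 to 12.6 mg/dL on the factor of 4.00, and 13.5 lies outside that range.
- Result: corrected calcium from 12.4 to 13.5 mg/dL (3.1 to 3.37 mmol/L) is markedly abnormal on the mmol/L half and not on the mg/dL half.

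The arithmetic does not show which of the two numbers was intended.

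**3. High glucose.**
- As printed: 250 × 18.016 = 4,504 mg/dL (4,545 on the table's own factor), against a printed 13.9.
- 13.9 / 18.016 = 0.77 mmol/L (0.76 on the table's own factor), against a printed 250. The halves differ by 4,504 / 13.9, a factor of about 324.
- Against the low line in mg/dL: 13.9 is below 40. A value between them is markedly high and markedly low at once, and every value that is not low is high.
- Against the low line in mmol/L: 250 / 2.2 is about 114 times the low limit.
- With the labels exchanged: 13.9 × 18.016 = 250.4 mg/dL against 250, agreement within 0.2%.

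**4. Other two-unit molar pairs**, with standard molar masses also assumed.

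| Line | Printed mg/dL | Converted, mmol/L | Printed mmol/L |
|---|---|---|---|
| Magnesium, low | 0.9 | 0.370 | 0.4 |
| Magnesium, high | 3 | 1.234 | 1.23 |
| Phosphate | 2 | 0.646 | 0.6 |
| Total cholesterol | 400 | 10.345 | 10.34 |
| Triglycerides | 500 | 5.647 | 5.7 |

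High magnesium, cholesterol and triglycerides agree within 1%. Low magnesium and phosphate differ by 7 to 8%, which rounding to one decimal explains. High calcium and high glucose are the only two faulty pairs.

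**The case against.** The strongest reply concerns status and reach, not arithmetic.

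- **The operative table is not in view.** The lines come from an amendment log, and the log does not always match the body. The per-protocol wording in Amendment 3, Change #6, names different medications from Section 3.5.4. The substudy threshold in the pharmacokinetics change of Amendment 1 is 10 subjects, while Section 9.1 has 5. That no change to Table 13-2 is logged therefore does not prove what Section 13.5 now says. This stands: that the faulty lines are in force is an inference.
- **Glucose may reach no output.** Table 10-1 plans no blood glucose, and the updated Table 13-2 also carries limits for other tests outside that panel, such as eGFR. This stands. A reader might infer from the printed glucose rule that the safety tables will flag nearly everyone or no one. The documents do not support that, since nothing shows that serum glucose will be analysed.
- **The calcium band is narrow and nothing is hidden.** The limit is for corrected calcium, Table 10-1 says only calcium, and no correction formula appears in the text at hand. Out-of-range values are flagged in the listings, and calcium has shift tables. This stands in part. It limits the damage, but the markedly abnormal table would still rest on an undetermined threshold.
- **The primary objective is not touched directly.** A reader might infer that the primary safety result is at risk. Under Section 2.2.1.1 the primary safety variable is the occurrence of TEAEs, which Table 13-2 does not define; laboratory values are among the other safety variables.

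**Conclusion.** The point holds, at modest weight. In the last stated text of Table 13-2 the high-calcium criterion is two different limits, 8.7% apart. Classification is undetermined for corrected values from 12.4 to 13.5 mg/dL. Calcium is a planned chemistry variable, so this can change counts in a planned table. How many subjects fall in the band cannot be estimated from the SAP.

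The high-glucose line is plainly a label exchange. It matters for output only if blood glucose is in the database.

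The conclusion assumes that the Section 13.5 body carries the same lines, and that calcium is tested against the corrected limit. The document does not show that any output has already been produced with the faulty limits, so no claim is made about reported results.

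**What to change.** 1. Check the Section 13.5 body for both lines.
2. Reconcile the high-calcium pair to one Grade 3 limit from the sponsor's CTCAE source (Section 10.2 names version 4.03 for adverse events). State it in matching mg/dL and mmol/L, and check that the ionized limit is of the same grade.
3. Exchange the unit labels on the high-glucose line, so that 250 goes with mg/dL and 13.9 with mmol/L. If blood glucose is not collected, delete the line.
4. Confirm that the laboratory programs use the corrected constants, in the unit of the analysis data, before the markedly abnormal listing and table are produced.

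The cost is two table lines and a check of two program constants, with no new data. Whether any calcium classification changes depends on the limit chosen and on the half now programmed.
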